18.4.2. EFFICACY DATA

The primary analysis will be performed on the mITT population. Analyses conducted using the PP will be considered supportive.

Primary Endpoint

In order to investigate whether the use of inhaled colistimethate sodium reduces the frequency of pulmonary exacerbations compared to placebo in subjects with NCFB chronically infected with *P. aeruginosa*, the following hypothesis will be tested:

- Null hypothesis A: there is no difference between inhaled colistimethate sodium and placebo as regards the effect on the pulmonary exacerbation rate against Alternative hypothesis A: inhaled colistimethate sodium reduces the pulmonary exacerbation rate.

The null hypothesis must be rejected for the efficacy of inhaled colistimethate sodium to be considered demonstrated.

A CCI analysis will be conducted using an alternative definition of NCFB pulmonary exacerbation. The re-classification of exacerbations will be conducted in a blinded fashion (before database lock). The alternative definition of pulmonary exacerbations used will be deterioration in three or more of the following key symptoms for at least 48 hours:

- Cough

Mean Annual Pulmonary Exacerbation Rate

The number of NCFB pulmonary exacerbations during the treatment period will be analysed using a Poisson regression model allowing for over-dispersion including treatment, pooled sites and use of stable concomitant therapy with oral macrolides as fixed effects and log-time on trial as an offset.

The number and the percentage of subjects with NCFB pulmonary exacerbations, the number of pulmonary exacerbations and the total follow-up time in years will be summarised by treatment group. The adjusted yearly mean exacerbation rates in each treatment group and the adjusted rate ratio with their 95% CIs will be estimated by the model.

For the analysis, 2 pulmonary exacerbations will be considered as a single episode in cases where the second exacerbation starts less than 14 days after the end of the antibiotic therapy (oral or intravenous) for the first pulmonary exacerbation.

If the null hypothesis will be rejected, additional investigation of proportionality of the hazard will be implemented in a secondary analysis. Additional details on the analysis will be provided in the SAP.

A corresponding two-sided p-value of <0.05 will be considered statistically significant.

Secondary Endpoints

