2.1 Primary Endpoint

The primary endpoint of this trial is the mean annual NCFB pulmonary exacerbation rate.

A pulmonary exacerbation is defined as the presence concurrently of at least 3 of the following 8 symptoms/signs for at least 24 hours:

- increased cough;
- increased sputum volume and/or consistency;
- increased sputum purulence;
- new or increased haemoptysis;
- increased wheezing;
- increased dyspnoea;
- increased fatigue/malaise;
- episodes of fever (temperature $\geq 38^{\circ}\text{C}$);

And it is clinically determined that the subject requires and is prescribed systemic antibiotic therapy.

The start date of a protocol-defined pulmonary exacerbation will be taken as the first day that at least 3 of the pre-defined 8 symptoms/signs occurred concurrently for at least 24 hours, as determined by the Investigator, as documented by the start date of the corresponding AE in the eCRF AE form.

Resolution of a pulmonary exacerbation is defined as the date of completion of the required course(s) of systemic antibiotic treatment and/or the Investigator's judgement that the NCFB pulmonary exacerbation has resolved, as documented by the end date provided for the corresponding AE in the eCRF AE form, whichever is the later of the two dates. The exacerbation end date will be reported at the next scheduled visit or by phone. A new pulmonary exacerbation is only considered to occur if there are at least 14 days between the end of the course of systemic antibiotics and the onset of new qualifying symptoms.

The treatment of pulmonary exacerbations will follow current treatment regimens used at the respective participating investigational site.

A supportive analysis will be conducted using an alternative definition of NCFB pulmonary exacerbation. The re-classification of exacerbations will be done in a blinded fashion (before

CONFIDENTIAL

Sponsor:	Zambon S.p.A.	Protocol Number:	Z7224L01
----------	---------------	------------------	----------

database lock). Alternative definition of pulmonary exacerbation: deterioration in three or more of the following key symptoms for at least 48 hours:

- Cough;
- Sputum volume and/or consistency;
- Sputum purulence;
- Breathlessness and/or exercise tolerance (dyspnoea);
- Fatigue and/or malaise;
- Haemoptysis;

And a physician determines a change in bronchiectasis treatment is required when other potential causes of clinical deterioration have been discounted.

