In the case of a partial onset date of NCFB pulmonary exacerbation due to missing day, the onset of the event will be assumed to be the first day of the month. If the resultant derived date is prior to the date of first IMP dose, then it will be assumed to be equal to the first IMP dose date. Resultant derived dates will be reviewed during the blind review meeting and documented in the Blind Data Review and Analysis Sets Report.

In case of a partial resolution date of NCFB pulmonary exacerbation due to missing day, the resolution of the event will be assumed to be the last day of the month. If the resultant derived date is after the treatment completion/discontinuation date, then it will be assumed to be equal to the treatment completion/discontinuation date.

In case a NCFB pulmonary exacerbation presents a symptom with missing duration, following a conservative approach, the longest duration based on the start and stop dates of that symptom and until the resolution date of the NCFB pulmonary exacerbation will be imputed.

Two NCFB pulmonary exacerbations will be considered as a single episode in the statistical analysis if the second exacerbation started less than 14 days after the end of the systemic antibiotic therapy for the previous exacerbation (start date of the exacerbation - end date of the treatment of the previous exacerbation < 14 days). In case of more than two exacerbations for the same subject, this rule will be applied iteratively (therefore, more than two exacerbations may be considered as a single episode). Such cases will be discussed during the blind review of the data and the decisions taken will be documented in the Blind Data Review and Analysis Sets Report.

The above rule will not apply to the analysis of NCFB pulmonary exacerbations as AEs in the safety analysis.

In case of NCFB pulmonary exacerbations considered as a single episode:

- the start date of the first event will be considered as the start date;
- the stop date of the last event will be considered as the stop date;
- a worst case approach will be considered for duration of symptoms and requirement of hospitalisation. For example, if one of two exacerbations considered as a single episode has/have increased dyspnoea for ≥ 24 hours and < 48 hours and the other one has increased dyspnoea for ≥ 48 hours, the single episode will be considered in the analysis as having dyspnoea for ≥ 48 hours.

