4.7.4.1 CCI Analysis Using Alternative Definition of NCFB Pulmonary Exacerbation

A CCI analysis will be conducted using an alternative definition of NCFB pulmonary exacerbation for the mITT Population. The re-classification of pulmonary exacerbations will be done during the blind review meeting and documented in the Blind Data Review and Analysis Set Report.

In this CCI analysis, a NCFB pulmonary exacerbation is defined as deterioration in three or more of the following key symptoms for at least 48 hours:

- Cough;
- Sputum volume and/or consistency;

CONFIDENTIAL

Sponsor:	Zambon S.p.A.	Protocol Number:	Z7224L01
----------	---------------	------------------	----------

- Sputum purulence;
- Breathlessness and/or exercise tolerance (dyspnoea);
- Fatigue and/or malaise;
- Haemoptysis;

And:

a physician determines a change in bronchiectasis treatment is required when other potential causes of clinical deterioration have been discounted, i.e. the subject requires a systemic antibiotic therapy due to the NCFB pulmonary exacerbation.

Subjects experiencing NCFB pulmonary exacerbations according to this alternative definition will be identified as those subjects having:

- An AE on the eCRF Adverse Events form with a MedDRA coded Preferred Term of “infective exacerbation of bronchiectasis” that is at least 48 hours in duration (i.e. stop date of AE – start date of AE + 1 \geq 2);
- At least 3 of the above symptoms on the eCRF Pulmonary Exacerbation Symptoms form for the Pulmonary Exacerbation Number corresponding to that AE, where those symptoms all occur between the start and stop dates of the AE;
- At least 1 therapy on the eCRF Systemic Antibiotic Therapy form for the Pulmonary Exacerbation Number corresponding to that AE.

Analysis will be conducted following the same rules and methods as detailed above for the main definition of NCFB pulmonary exacerbations.

4.7.4.2 **CCI** Analysis for Discontinuers

In order to assess the potential impact of missing data on the results of the primary efficacy analysis, **CCI** analyses based on multiple imputation (MI) will be performed on all mITT subjects based on the approach proposed by Keene et al. ^[1].

For all subjects with a follow-up duration shorter than 365 days (i.e., 52 weeks + 1 day), the number of pulmonary exacerbations from the end of the follow-up period up to day 365 will be imputed.

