4.13 Changes in Conduct or Planned Analyses from the Protocol

Sections 2.2, 4.4.11, 4.7.5 and 4.7.6.3: The protocol incorrectly referred to the units for the determination of CCI [REDACTED] which have been reported as CCI [REDACTED] by the central laboratory.

Section 3.9: The rationale and results for a reassessment of the original sample size calculation are provided to explain the reduced target sample size and associated levels of power.

Section 4.7.4: The protocol states that the Negative Binomial Model will consider the log-time on study as offset. However, as specified in Section 4.1.7, NCFB Pulmonary Exacerbations analyses focus on the treatment period so log-time on treatment will be considered.

Section 4.7.6.1: The protocol states that CCI [REDACTED] = CCI [REDACTED]. For time-to-event endpoints, generally the + 1 is not included because this overestimates the time by 1 day for every event, therefore "+ 1" has been deleted.

Section 4.7.6.4: The protocol states that any episodes of pneumonia will be considered as severe pulmonary exacerbations. Any reported episodes of pneumonia which do not require intravenous antibiotics and/or hospitalisation will be data queried to amend the Preferred Term. However, any pulmonary exacerbation on the Pulmonary Exacerbation form of the eCRF that is linked to an adverse event with a Preferred Term of 'Pneumonia' but does not have any CCI [REDACTED] or CCI [REDACTED] will be assumed to be a severe NCFB pulmonary exacerbation.

Section 4.7.6.5: The protocol states that the CCI [REDACTED] total score will be computed and analysed. However, as recommended in the Manual Scoring Instructions CCI [REDACTED] only the CCI [REDACTED] domain scores will be presented and analysed.

There have been no other changes in analyses from those defined in the protocol.

CONFIDENTIAL

Sponsor:	Zambon S.p.A.	Protocol Number:	Z7224L01
----------	---------------	------------------	----------

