  'Col. Sodium / Placebo: Visit 6' 0 0 1 0 0 0 -1 0,
  'Col. Sodium / Placebo: Visit 7' 0 0 0 1 0 0 0 -1 / cl;
  BY byvar; (optional)
  WHERE wherever; (optional)
RUN;
```

Notes:

- Visit represents the clinic visit;
- Psite represents the pooled site, i.e. country, as detailed in [Section 4.9.1](#);
- Med represents use of stable concomitant therapy with oral macrolides (e.g. azithromycin or erythromycin or clarithromycin) (Yes/No);
- Sub represents the Subject Number;
- Change represents the change from baseline to each visit of the variable;
- Baseline represents the baseline value of the variable;
- Treatment order: 1= Colistimethate Sodium, 2= Placebo.

CONFIDENTIAL

Sponsor:	Zambon S.p.A.	Protocol Number:	Z7224L01
----------	---------------	------------------	----------

- **Tables that require Prentice, Williams and Peterson Total Time model and 95% CIs of hazard ratios between treatments:**

```
PROC PHREG data=dset;
  CLASS treatment psite med;
  MODEL (tstart , tstop)*status(1) = treatment psite med / ties=Breslow;
  STRATA episode;
  HAZARDRATIO 'Col. Sodium vs Placebo' treatment / cl=both;
  BY byvar; (optional)
  WHERE wherever; (optional)
RUN;
```

Notes:

- Psite represents the pooled site, i.e. country, as detailed in [Section 4.9.1](#);
- Med represents use of stable concomitant therapy with oral macrolides (e.g. azithromycin or erythromycin or clarithromycin) (Yes/No);
- Status represents the censoring indicator (1 = censored);
- Treatment order: 1= Colistimethate Sodium, 2= Placebo;
- Dataset for the analysis should be adequately created: Subjects with no events have a single observation, while subjects with one event have two rows etc... A pair of variables (tstart, tstop) is used to define the time interval of risk. The start time (tstart) is generally equal to 0 for the first event and equals to the last recurrence stop time for further events. During an episode of pulmonary exacerbation, the subjects can't have another episode. Therefore, they are by definition not at risk for a next event during a previous episode. The stop time (tstop) is a recurrent event time (status = 1) or a censored time (status = 0). The event order should be denoted by variable episode.

- **Multiple Imputation for pulmonary exacerbation rate**

An example of SAS code is provided below for the **CCI** analyses pulmonary exacerbation rate.

Missing at random and copy reference imputation

```
PROC GENMOD DATA=dataset1;

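### Two non-primary analyses of exacerbations have written rules that contradict themselves: the 48-hour event rule accepts shorter events, and the PWP status variable is coded two opposite ways

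*SAP*

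**What the plan says.** **Alternative definition (supportive).** Protocol 18.4.2 states that the alternative definition "used will be deterioration in three or more of the following key symptoms for at least 48 hours". SAP 2.1 repeats it as "deterioration in three or more of the following key symptoms for at least 48 hours", and SAP 4.7.4.1 opens with the same requirement. SAP 4.7.4.1 then gives the rule for finding these events. It asks for:

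- a coded adverse event (AE) "that is at least 48 hours in duration (i.e. stop date of AE" minus its start date, plus 1, is 2 or more;
- at least three listed symptoms, "where those symptoms all occur between the start and stop dates of the AE";
- at least one systemic antibiotic.

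SAP 4.7.4 also handles symptom duration directly. Where it is missing, the SAP imputes "the longest duration based on the start and stop dates of that symptom" and up to resolution. For merged episodes, its worked example separates dyspnoea of "24 hours and < 48 hours and the other one has increased dyspnoea for" 48 hours or more.

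**PWP model (exploratory, SAP 4.7.4.7).** The code in SAP 4.14 is "MODEL (tstart , tstop)*status(1) = treatment psite med / ties=Breslow". In PROC PHREG the value in parentheses is the censoring value, and the variable note below the code agrees that 1 means censored. The note on building the dataset, in the same list, says the reverse: 1 marks a recurrent event and 0 a censored time.

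**The concern.** The longer duration is one of the features meant to set the alternative definition apart from the 24-hour primary definition. Leaving out wheeze and fever is another. If the duration is not enforced, Table 14.2.1.1.3 tests robustness to a stricter event less than its label suggests.

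For the PWP model the dataset note is the only instruction on how to build the data. A programmer who follows it and runs the printed code would treat exacerbations as censored and end of follow-up as the event. Table 14.2.1.4 would then carry a hazard ratio for the wrong outcome under the heading of exacerbations.

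SAP Addendum section 3 says that internal consistency is being examined because the application may rest on a single pivotal study, so supportive tables carry some weight.

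**Working it through.** **1. The 48-hour rule.** The inputs are the date rule and the 48-hour requirement, both in SAP 4.7.4.1. If stop date minus start date is d days, elapsed time lies between max(0, 24(d − 1)) and 24(d + 1) hours.

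| d | d + 1 | Passes (≥ 2)? | Elapsed hours | Can reach 48 h? | Sure to reach 48 h? |
|---|---|---|---|---|---|
| 0 | 1 | no | 0–24 | no | no |
| 1 | 2 | yes | 0–48 | no | no |
| 2 | 3 | yes | 24–72 | yes | no |
| 3 | 4 | yes | 48–96 | yes | yes |

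The SAP's equation is reproduced only as a nominal day count (2 dates × 24 h = 48 h), not as elapsed time. The d = 1 row is accepted although it always falls short.

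Assuming start times uniform over the day, the share accepted by true duration is:

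| True duration | d + 1 ≥ 2 (printed) | d + 1 ≥ 3 | d + 1 ≥ 4 |
|---|---|---|---|
| 12 h | 50% | 0% | 0% |
| 24 h | 100% | 0% | 0% |
| 36 h | 100% | 50% | 0% |
| 47 h | 100% | 96% | 0% |
| 48 h | 100% | 100% | 0% |

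A threshold of 3 is the highest that loses no true 48-hour event, but it still admits some shorter ones. A threshold of 4 admits none shorter but loses true events. Dates alone cannot apply the definition exactly.

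The symptom condition adds no duration test. Three symptoms of any length inside the AE dates satisfy it.

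**2. The PWP coding.** In SAP 4.14:

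| Place | status = 1 means |
|---|---|
| PWP model statement | censored |
| PWP variable note | censored |
| PWP dataset note | event |
| Matching indicator, Kaplan-Meier and Cox notes | censored |

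The dataset note is the outlier. SAP 4.14 does label some code as examples only, but that sentence covers descriptive statistics and frequency counts, not this model.

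To size the effect of following both instructions literally, a PWP total-time model was simulated with episode strata and Breslow ties. From SAP 3.9 come the rates 1.2701 and 0.8256 per year (0.8256/1.2701 = 0.65), dispersion 0.273 and 188 subjects per arm. Dropout, equal in both arms, is an assumption. Episodes were capped at the 90th percentile of events, as SAP 4.7.4.7 describes; 500 trials were run per setting.

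| Dropout | HR, consistent coding | HR, inverted coding | Modelled events placebo/active, consistent | Modelled events placebo/active, inverted |
|---|---|---|---|---|
| 10% | 0.685 | 0.994 | 200/139 | 147/167 |
| 20% | 0.680 | 0.998 | 185/129 | 143/164 |
| 30% | 0.683 | 0.996 | 169/120 | 140/161 |

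A separate simulation of 100 trials, with 15% dropout and up to four episodes, gave median HRs of 0.68 (5th to 95th percentile 0.56 to 0.80) and 1.00 (0.85 to 1.16). At 20% dropout the totals are 185 + 129 = 314 and 143 + 164 = 307. The total would therefore not reveal an inversion, but the counts by arm would.

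**The case against.** **The 48 hours may belong to the episode.** SAP 4.2.1 clarifies the primary definition in this way: the episode must last 24 hours, while a single symptom may be shorter. The alternative rule has the same structure, and SAP 4.7.4.1 says the analysis follows the rules and methods of the main definition. This stands in part. A reader might infer that every symptom must last 48 hours and that the symptom condition is plainly wrong. The documents do not settle that. SAP 4.2.1 speaks only of the primary definition, while the alternative definition attaches the time to the symptoms and SAP 4.7.4 classifies symptom duration at 48 hours. The SAP needs to say which reading it means. The adjacent-date error holds under either.

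**Few events are likely to be affected.** Every qualifying event needs systemic antibiotics, and Protocol 9.1.5 speaks of an initial 14-day course, so an AE confined to two dates is probably rare. This stands.

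**Blind review may have dealt with it.** Re-classification was planned under blinding, before database lock, with its own report. This also stands. A reader might infer that Table 14.2.1.1.3 is wrong, but the documents do not show which rule was applied.

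**The PWP conflict may be one stray sentence.** Everything else in SAP 4.14 treats 1 as censored, and an HR near 1.0 beside a positive primary result would probably have been noticed. A reader might infer that Table 14.2.1.4 was run inverted; nothing in the documents supports that. The contradiction in the text remains.

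**Conclusion.** Both rules are wrong as written, and both are minor. The date rule accepts AEs that cannot last 48 hours, and this rests on arithmetic alone. The two PWP notes cannot both be followed with the printed code, and this rests on the text alone. The size of the first is not in the documents and is probably small. The second matters only if the data were built by the dataset note and run with the printed code. The fall from about 0.68 to about 1.0 is illustrative and depends on the planning rates and the assumed equal dropout; it is not a trial result.

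The primary negative binomial analysis uses the main event definition and neither of these rules, so its result is not in question.

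**What to change.** **Alternative definition.**

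1. Check the Blind Data Review and Analysis Sets Report for the rule actually applied.
2. State in the SAP text whether the 48 hours applies to the symptoms or to the episode.
3. If the review enforced 48 hours, correct the text only.
4. If the printed date rule was used, replace it with the recorded symptom-duration category (48 hours or more) for at least three listed symptoms. If only dates exist, require stop minus start plus 1 to be at least 3, and say that this is approximate.
5. In that case keep the blinded classification as it stands, and add a rerun of Table 14.2.1.1.3 as a labelled post hoc sensitivity result, since the trial is unblinded.

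**PWP model.**

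1. Define status once, so that the dataset note, the variable note and the value in the model statement agree.
2. Check that modelled events in each arm of Table 14.2.1.4 equal that arm's exacerbation count after the episode cap.
3. Rerun the table only if they do not, and document it as an error correction.

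The certain cost is two text corrections and two checks of existing records. At most two tables need a rerun. No new data are needed if symptom durations are on the eCRF, as SAP 4.7.4 implies. Slightly fewer events may qualify under a corrected 48-hour rule.

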4.7.4.3 CCI Analysis on Adherent Subjects

The primary analysis will also be repeated considering the subgroup of mITT subjects who were considered adherent, i.e. had an adherence of at least 80%.

4.7.4.4 Further Investigation: Number of Pulmonary Exacerbations in the 12 Months Prior to Study Entry

To further investigate any possible factor that might affect the mean annual NCFB pulmonary exacerbation rate, an exploratory negative binomial model will be fitted for the mITT population considering as an extra covariate the number of NCFB pulmonary exacerbations requiring oral or intravenous antibiotics in the 12 months prior to study entry.

4.7.4.5 Further Investigation: Stratified Analysis by Number of Pulmonary Exacerbation Requiring Oral or Intravenous Antibiotics in the 12 Months Prior to Study Entry

The number of NCFB pulmonary exacerbations requiring oral antibiotics in the last 12 months and the number of NCFB pulmonary exacerbations requiring intravenous antibiotics in the last 12 months prior to study entry, as collected in the eCRF Screening folder on the Non-CF Bronchiectasis History form, will be summed.

Analysis will be performed with the same criteria and methods as described for the primary efficacy model. If a subject has no data regarding the number of NCFB pulmonary exacerbations requiring oral and/or intravenous antibiotics in the last 12 months prior to study entry the subject will be excluded from the analysis.

A stratified analysis will also be performed classifying subjects according to the number of pulmonary exacerbations requiring oral or intravenous antibiotics in the 12 months prior to study entry, as reported in [Section 4.1.5](#).

4.7.4.6 Further Investigation: Stratified Analysis by Previous Usage of Colistimethate Sodium/Colistin

A stratified analysis will also be performed by previous usage of colistimethate sodium/colistin (as collected on the Non-CF Bronchiectasis History eCRF form) as reported in [Section 4.1.5](#).

